Pharmacodynamics: Hyperphosphatemia is a common drug-induced toxicity due to renal tubular FGFR inhibition and, thus, it can serve as a pharmacodynamics marker of drug activity. Dose dependent elevations in serum phosphate occurred in all patients starting at 4 mg daily. Because this represents a target-mediated drug effect, one of the Phase 1 study goals was to select a dose regimen that consistently induced manageable hyperphosphatemia but did not exceed a critical level requiring cessation of therapy, which in the Phase 1 study was 7 mg/dL. Emerging data from the ongoing Phase 1 study indicates that a phosphate increase of at least 35% over baseline level may be associated with anti-tumor response. Therefore a pharmacodynamics objective of 50% increase in phosphate level over baseline was felt to be appropriate. Considering the median phosphate level of 3.6 mg/dL at baseline in the Phase 1 study, and of 3.3 mg/dL at baseline in the Phase 2 study (IA1 data) an increase of at least 50% for the majority of subjects would correspond to an absolute phosphate level of around 5.5 g/dL (which is also 35% over the phosphate ULN). Subjects achieving a phosphate level of less than 5.5 mg/dL by the end of first cycle dosing period (day 28) would be considered to have had inadequate PD effect and would be candidates for dose escalation to 9 mg daily to achieve an optimum PD effect (phosphate range 5.5-7 mg/dL).

Overall, emerging pharmacokinetic/pharmacodynamics (PK/PD) modeling suggests that approximately 60% of subjects would have serum phosphate levels < 5.5 mg/dL (on Day 28) when dosed with 6 mg and would potentially benefit from dose up-titration. Additionally, by Day 28 approximately 13% of subjects may reach a phosphate level \geq 7 mg/dL and thus need an unscheduled interruption of up to 7 days to maintain the phosphate level in the target range of 5.5 to <7 mg/dL.

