3.4 Dose Modifications

All toxicity grades below are described using the NCI Common Terminology Criteria for Adverse Events (CTCAE) version 5.0.

All appropriate treatment areas should have access to a copy of the CTCAE version 5.0. A copy of the CTCAE version 5.0 can be downloaded from the CTEP website

(http://ctep.cancer.gov/protocolDevelopment/electronic_applications/ctc.htm)

Dose Modifications and Dose Delays

Treatment can be modified or terminated based on toxicity as described in Table 1. For eye, skin/nail, dry mouth/mucositis, liver, and phosphate toxicity, specific recommendations in the management guidelines are provided below.

Table 1: Dose Modification Guidelines

Toxicity Grade	Action	Dose Modification After Resolution of Adverse Event
1	None	Continue same dose
2	None or consider interruption	If interrupted, restart at same dose or 1 dose lower, if necessary.
3	Interrupt drug	Restart at 1 or 2 doses lower if recovery (to \leq Grade 1 or back to baseline for non-hematologic toxicity) is within 28 days. Discontinue drug if unresolved for >28 days.
4	Interrupt drug or discontinue	Discontinue*

For general toxicity management:

- Subjects with any grade of toxicity (Grade 1 to 4) should be provided symptomatic treatment when applicable.
- Subjects should follow the guidelines in Table 2 for dose reduction recommendations and may have more than 1 dose reduction.
- If JNJ-42756493 (erdafitinib) must be withheld for more than 28 days for a drug-related adverse event that fails to resolve to acceptable level (e.g., \leq Grade 1 non-hematologic toxicity or back to baseline), treatment with JNJ-42756493 (erdafitinib) should be discontinued with the exception noted below.*
- If the subject achieves calcium-phosphate product $> 70 \text{ mg}^2/\text{dL}^2$ for 2 consecutive weeks despite phosphate lowering therapy or $> 90 \text{ mg}^2/\text{dL}^2$ any time during treatment despite phosphate lowering therapy, JNJ-42756493 (erdafitinib) should be withheld until recovery to calcium-phosphate product $< 55 \text{ mg}^2/\text{dL}^2$. Treatment may be reintroduced at the first reduced dose level.
- In all cases of clinically significant impaired wound healing or imminent surgery or potential bleeding complications, it is recommended that dose administration be interrupted, appropriate clinical laboratory data be carefully monitored, and supportive therapy administered, where applicable. Dose

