If a subject meets the liver event stopping criteria, the study drug should not be re-administered. In the case in which Hy's law is not met and the investigator can demonstrate that re-introduction of study drug is in the best interest of the subject considering the terminal nature of the disease, the drug may be re-introduced at a lower dose and/or intensity if the medical monitor is in agreement with this assessment. With appropriate re-consenting, the subject can be retreated with a 1- or 2-dose level reduction as appropriate, along with appropriate clinical follow-up as designated by the investigator. Prior to re-introduction, the investigator should obtain written permission from the study medical monitor and the IRB. The investigator should also have the subject re-consent, explaining that re-introduction of study drug could lead to liver damage, which may be serious and/or may even result in death.

Guidelines for the Management of Elevated Phosphate Levels

Guidelines for the clinical management of elevated serum phosphate levels are presented in Table 3.

Table 3: Guidelines for Management of Serum Phosphate Elevation

Serum Phosphate Level	Study Drug Management	Medical Management
All subjects in the study	Continue JNJ-42756493 (erdafitinib) treatment.	Restriction of phosphate intake to 600 – 800 mg/day.
5.5-6.9 mg/dL (1.8-2.2 mmol/L)	Continue JNJ-42756493 (erdafitinib) treatment.	Restriction of phosphate intake to 600 – 800 mg/day. May consider sevelamer 800 mg to 1,600 mg 3 times a day (with food)
7.0-9.0 mg/dL (2.3-2.9 mmol/L)	Withhold ^a JNJ-42756493 (erdafitinib) treatment until serum phosphate level returns to < 5.5 mg/dL. Re-start treatment at the same dose level. A dose reduction may be implemented for persistent ^b hyperphosphatemia (≥ 7 mg/dL) if clinically necessary	Restriction of phosphate intake to 600 – 800 mg/day. Sevelamer 800 to 1,600 mg 3 times a day with food until phosphate level is < 5.5 mg/dL.
> 9.0 mg/dL (> 2.9 mmol/L)	Withhold ^a JNJ-42756493 (erdafitinib) treatment until serum phosphate level returns to < 5.5 mg/dL. Re-start treatment at the first reduced dose level. A second dose reduction may be implemented if needed or clinically indicated for persistent ^b hyperphosphatemia (≥ 7 mg/dL) at every cycle	Restriction of phosphate intake to 600 – 800 mg/day. Sevelamer up to 1,600 mg 3 times a day with food AND Acetazolamide 250 mg 2 or 3 times a day only until serum phosphate level returns to < 5.5 mg/dL.

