> 10.0 mg/dL (> 3.2 mmol/L) and/or significant alteration in baseline renal function and/or Grade 3 hypocalcemia	JNJ-42756493 (erdafitinib) should be discontinued permanently. (In situations where the subject is having clinical benefit and the investigator and the sponsor's medical monitor agree that re-starting drug is in the best interest of the subject, the drug may be re-introduced at 2 dose levels lower if appropriate ^c . Follow other recommendations described above.)	Medical management as clinically appropriate.
NOTE: These are general guidelines that are based on emerging data and consensus experience of participating investigators and/or the experts in the field. The treating physicians must use clinical judgment and local standard of care to decide the best way to manage phosphate elevation. If Sevelamer hydrochloride (renagel) is not available, use of other phosphate binders (non-calcium containing) based on the local standard is recommended, including Sevelamer carbonate (Renvela) or lanthanum carbonate (Fosrenol). These guidelines will be updated based on emerging data. Additional information on phosphorous in foods by class of food can also be found at www.permanente.net/homepage/kaiser/pdf/42025.pdf . Additional information for phosphate management and diet can be found the National Kidney Foundation website (http://www.kidney.org/atoz/content/phosphorus.cfm)		

Table 3: Guidelines for Management of Serum Phosphate Elevation

a Drug interruptions for hyperphosphatemia suggested to be 7 days duration

b Persistent hyperphosphatemia is considered to be more than 1 sequential phosphate value of ≥ 7 mg/dL

c If a subject has been deriving benefit from treatment, and the investigator can demonstrate that re-introduction of study drug is in the best interest of the subject considering the terminal nature of the disease, the drug may be re-introduced at a lower dose and/or intensity if the medical monitor is in agreement with this assessment. With appropriate re-consenting, the subject can be retreated with a 1- or 2-dose level reduction as appropriate, along with appropriate clinical follow-up as designated by the investigator. Prior to re-introduction, the investigator should obtain written permission from the study medical monitor and the IRB. The investigator should also have the subject re-consent, explaining that re-introduction of study drug could lead to increased risk of recurrent toxicities. (please see Section 16.2.3 for details)

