4.1 Therapeutic Parameters for JNJ-42756493 (Erdafitinib) Treatment

NOTE: In addition to the study parameters listed in the MATCH Master Protocol, the below parameters must also be performed for patients receiving JNJ-42756493 (erdafitinib) treatment.

NOTE: All assessments required prior to registration to treatment should be done \leq 4 weeks prior to registration to Steps 1, 3, 5, 7, excluding the radiologic evaluation and electrocardiogram (ECG).

Test/Assessment	Prior to Registration to Treatment	Treatment			End of Treatment	Follow Up ^F
		Every Cycle, prior to treatment	Cycle 1 Day 15	Every 2 Cycles		
H&P, Weight, Vital signs ^A	X	X ^J	X			X
Performance status	X	X ^J	X			X
CBC w/diff, plt ^B	X	X ^J	X			X
Serum chemistry ^B	X	X ^J	X			X
Radiologic evaluation ^D	X		X ^D			X ^F
β -HCG ^C	X					
Toxicity Assessment ^G		X	X	X	X	X ^F
Pill Count/Diary ^H			X			X
ECG ^K	X	X ^I				
Ophthalmologic exam ^L	X	X			X	
Phosphate Levels ^M			X			
Tumor biopsy and blood sample for MATCH Master Protocol ^E				X	X	X

- History and physical, including vital signs and weight at the start of each cycle (up to 3 days before start of new cycle).
- Albumin, alkaline phosphatase, total bilirubin, bicarbonate, BUN, calcium, creatinine, glucose, phosphorus, potassium, SGOT[AST]^J, SGPT[ALT]^J, sodium, magnesium and serum tumor markers (including LDH, PSA if appropriate). Serum tumor markers are not required on Cycle 1, Day 15. For eligibility purposes, participants with creatinine levels above institutional normal, Cockcroft-Gault will be used to calculate creatinine clearance. CBC w/diff, platelets and serum chemistries should be performed on cycle 1, day 1 (or up to 7 days prior), and at the start of each subsequent cycle (up to 3 days before start of new cycle). CBC with differential will be performed more frequently in patients with grade 4 neutropenia or thrombocytopenia until resolution to \leq grade 3. CBC and serum chemistries are only required in follow-up until values return to pre-treatment levels or until progressive disease.
- Blood pregnancy test (women of childbearing potential) required prior to beginning treatment.

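### Section 3.4 gives two rules for high phosphate with no order of precedence; they conflict on restart or discontinuation when the calcium-phosphate product exceeds 90, and scheduled chemistry can test the two-week trigger at most once

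*Protocol*

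**What the plan says.** Protocol Section 3.4 handles raised phosphate in two places.

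- **Product rule (general toxicity management bullets).** The triggers are a calcium-phosphate product above 70 mg²/dL² "for 2 consecutive weeks despite phosphate lowering therapy", or above 90 "any time during treatment despite phosphate lowering therapy". Drug "should be withheld until recovery to calcium-phosphate product" below 55, and then: "Treatment may be reintroduced at the first reduced dose level".
- **Table 3 (phosphate alone).** At 5.5-6.9 mg/dL treatment continues. At 7.0-9.0 it is withheld until phosphate is below 5.5, then: "Re-start treatment at the same dose level"; a reduction is optional if the elevation persists. Above 9.0 it is withheld until below 5.5 and restarted at the first reduced level. Above 10.0 it is stopped permanently, with an exception for clinical benefit that allows a restart two levels lower. Footnote a adds: "Drug interruptions for hyperphosphatemia suggested to be 7 days duration".

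Section 3.4 refers phosphate toxicity to the specific guidelines further down, but neither place says which prevails when both apply.

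Section 4.1 schedules serum chemistry, including calcium and phosphorus, at Cycle 1 Day 1 (or up to 7 days before), at Cycle 1 Day 15, and then "at the start of each subsequent cycle (up to 3 days before start of new cycle"). These are in addition to the parameters of the Master Protocol.

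**The concern.** Hyperphosphatemia is an expected on-target effect of this drug: Section 1.3 uses it as the pharmacodynamic marker, and Section 3.3 lists it as likely. Rules on raised phosphate will therefore drive holds and dose changes. If two instructions apply to one set of laboratory values and lead to different actions, two sites can each follow the written protocol and treat the same patient differently. One may restart at the same dose and the other a level lower, or one may stop permanently where the other resumes. That is a safety question, and it also makes dose intensity depend on which paragraph a site applied. A trigger defined over two weeks also needs measurements close enough together to show it.

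**Working it through.** **Inputs.** Product thresholds 55, 70 and 90 mg²/dL² (Section 3.4 bullets). Phosphate cut-offs 5.5, 7.0, 9.0 and 10.0 mg/dL (Table 3). Dose levels from Table 2. Chemistry schedule from Section 4.1. The protocol gives no calcium value with the product rule, so calcium is an assumption, shown for 8.0 to 11.0 mg/dL. There is no stated figure to reproduce.

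**Step 1: put both rules on one scale.** Phosphate equivalent = product threshold ÷ calcium.

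| Calcium (mg/dL) | 55 ÷ Ca | 70 ÷ Ca | 90 ÷ Ca |
|---|---|---|---|
| 8.0 | 6.88 | 8.75 | 11.25 |
| 9.0 | 6.11 | 7.78 | 10.00 |
| 9.5 | 5.79 | 7.37 | 9.47 |
| 10.0 | 5.50 | 7.00 | 9.00 |
| 10.5 | 5.24 | 6.67 | 8.57 |
| 11.0 | 5.00 | 6.36 | 8.18 |

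The thresholds match 5.5, 7.0 and 9.0 only at calcium 10.0. On either side of that value the rules separate.

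**Step 2: restart and discontinuation when the product exceeds 90.**

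- *Phosphate 7.0-9.0.* At the top of the band this needs calcium above 90 ÷ 9.0 = 10.0; at phosphate 8.0 it needs calcium above 90 ÷ 8.0 = 11.25. Example: 8.8 × 10.3 = 90.6. Table 3 restarts at the same dose; the product rule resumes at the first reduced level. By Table 2 that is 8 against 6 mg (2 ÷ 8 = 25%) or 9 against 8 mg (1 ÷ 9 = 11%).
- *Phosphate above 9.0 up to 10.0.* Both name the first reduced level. There is no conflict on restart dose.
- *Phosphate above 10.0.* At 10.1 this needs calcium above 90 ÷ 10.1 = 8.91. Example: 10.1 × 9.0 = 90.9. Table 3 stops permanently, and its exception requires medical monitor and IRB permission and re-consent. The product rule allows reintroduction at the first reduced level and states no such conditions.

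**Step 3: recovery.**

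- 5.8 × 9.2 = 53.4: recovered by the product (below 55), not by Table 3 (phosphate not below 5.5).
- 5.4 × 10.3 = 55.6: recovered by Table 3, not by the product.

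**Step 4: can scheduled chemistry show two weeks above 70?**

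- Cycle 1 Day 1 precedes drug effect, so Day 1 to Day 15 is not an on-treatment pair.
- Cycle 1 Day 15 to Cycle 2 Day 1 (day 29): 29 − 15 = 14 days, or 26 − 15 = 11 days if the three-day window is used. This is one usable pair at most.
- From Cycle 2 Day 1 onward the gap is 28 days, or 25 to 31 days with the window. No scheduled pair can show a two-week elevation.

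Table 3 implies unscheduled checks, since drug is held until phosphate falls, but it sets no interval. For liver events Section 3.4 does set one: a repeat within 2 to 3 days, then monitoring once or twice weekly.

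**The case against.** The strongest reply is that the two rules are cumulative safeguards. A site can hold when either triggers and resume only when both have recovered. That resolves most hold and recovery differences, including phosphate 6.9 with calcium 10.2 (product 70.4), where Table 3 continues and the product rule holds after two weeks. But the protocol nowhere says to read them together, and doing so does not settle the restart dose or whether to discontinue.

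It can also be said that Table 3 calls itself general guidance subject to clinical judgment, and that the product rule says only that treatment may be reintroduced. This softens the conflict but does not remove it. Nor does treating Table 3 as the specific rule that overrides the general one: the product bullet is itself specific to phosphate, and no such ranking is given.

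Four stronger readings are tempting, and the documents do not support them.

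- *That the restart doses conflict across most of the 7.0-9.0 band at ordinary calcium.* At calcium 9.5 and phosphate 8.0 the product is 76.0, so only the two-week trigger could apply, and only on phosphate-lowering therapy. By then Table 3 has already withheld drug, and it permits a reduction for persistent elevation. Both rules then allow a lower dose.
- *That the two-week trigger can never be observed.* Cycle 1 Day 15 to Cycle 2 Day 1 is one on-treatment pair. The Master Protocol, not at hand, may add samples.
- *That Section 1.3 sets a third hold rule.* Its remark that some subjects would "need an unscheduled interruption of up to 7 days to maintain the phosphate level in the target range of 5.5 to <7 mg/dL" is modelling in a dose rationale, not a management instruction.
- *That about 13% of subjects are affected.* That figure in Section 1.3 follows a sentence about dosing at 6 mg, and it counts everyone at or above 7 mg/dL, not those for whom the rules disagree.

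**Conclusion.** The point stands in a limited form. Section 3.4 holds two sets of instructions for raised phosphate without an order of precedence. They conflict on restart dose when the product exceeds 90 with phosphate 7.0-9.0, which requires calcium above 10.0 mg/dL. They conflict on discontinuation when phosphate is above 10.0 with the product above 90, which can happen at calcium of about 9. The second is the starker conflict because it needs no raised calcium. The recovery criteria can disagree in either direction.

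On this subprotocol's own schedule, the two-week trigger is assessable at most once and not from cycle 2 onward.

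All examples rest on assumed calcium values and on the patient already receiving phosphate-lowering therapy, as the product rule requires. How many patients would fall in a conflict zone cannot be derived from the protocol. Which clinical rule is right is not judged here. The point should be corrected; it does not put the trial's primary question at risk.

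**What to change.** Reconcile the product rule in the general toxicity bullets of Section 3.4 with Table 3 and its footnotes. For values that fall under both, state which governs (a) the hold, (b) recovery, and (c) restart dose or discontinuation, and cross-reference each place to the other. Align the two-week trigger with how often calcium and phosphate are measured, so that a site can tell from its own results whether the trigger is met; if the Master Protocol already requires the samples, a reference to it is enough. The clinical thresholds and actions are for the sponsor to decide.

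The cost is a wording change and possibly a repeat chemistry in patients who have had a high value.

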JNJ-42756493 (Erdafitinib) in Patients with Tumors with
FGFR Amplifications

JNJ-42756493 (ERDAFITINIB) TREATMENT [name]
SUBPROTOCOL CHAIR:

JNJ-42756493 (ERDAFITINIB) TREATMENT [name]
SUBPROTOCOL CO-CHAIR:

JNJ-42756493 (ERDAFITINIB) TRANSLATIONAL [name], PhD
CHAIR:

Version Date: March 11, 2019

**NOTE: This subprotocol (EAY131-K1) should
be used in conjunction with the
MATCH Master Protocol (EAY131).**

SUBPROTOCOL ACTIVATION DATE
Incorporated in Addendum #13
Addendum #16
Addendum #19

Agent	IND#	NSC#	Supply
JNJ-42756493 (Erdafitinib)	IND Sponsor: DCTD, NCI IND# [REDACTED]	781558	NCI Supplied

Table of Contents

Molecular Analysis for Therapy Choice (MATCH)	i
MATCH Treatment Subprotocol K1: Phase 2 Study of JNJ-42756493 (Erdafitinib) in Patients with Tumors with FGFR Amplifications	1
Table of Contents	2
Schema	4
1. Introduction	5
1.1 JNJ-42756493 (Erdafitinib)	5
1.2 Supporting Preliminary Data	8
1.3 Rationale for 8 mg starting and 9 mg up-titration dose:	9
2. Selection of Patients	12
2.1 Eligibility Criteria	12
3. JNJ-42756493 (Erdafitinib) Treatment Plan	15
3.1 Administration Schedule	15
3.2 Adverse Event Reporting Requirements	16
3.3 Comprehensive Adverse Events and Potential Risks List (CAEPR) for JNJ-42756493 (Erdafitinib, NSC 781558)	19
3.4 Dose Modifications	23
3.5 Supportive Care	33
3.6 Duration of Agent-specific treatment	33
3.7 Duration of Follow-Up	34
4. Study Parameters	35
4.1 Therapeutic Parameters for JNJ-42756493 (Erdafitinib) Treatment	35
5. Drug Formulation and Procurement	38
5.1 JNJ-42756493 (NSC 781558)	39
6. Translational Studies	42
7. References	42
Appendix I Patient Pill Calendar	43
Appendix II Actionable Mutations for Sub-Protocol EAY131-K1	46
Appendix III Patient Drug Information Handout and Wallet Card	47

TREATMENT SUBPROTOCOL CHAIR

[name]
Samuel Oschin Comprehensive Cancer Institute
Cedars-Sinai Medical Center
[name]
[name]
[name]
[contact]
[contact]
Email: [contact]

[figure not shown]
TREATMENT SUBPROTOCOL CO-CHAIR

[name]
Vanderbilt University
Ingram Cancer Center
[name]
[name]
[name]
[contact]
[contact]
Email: [contact]

TRANSLATIONAL CHAIR

[name], PhD
University of Washington
[name]
[name]
[contact]
[contact]
Email: [contact]

Schema

Cycle = 28 days
Accrual Goal: 35
*Refer to Section 3.1

1. Introduction

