administration may be restarted when it is considered safe and at an appropriate dose, according to the investigator's assessment.

*Exception: if a subject has been deriving benefit from treatment, and the investigator can demonstrate that re-introduction of study drug is in the best interest of the subject considering the terminal nature of the disease, the drug may be re-introduced at a lower dose and/or intensity if the medical monitor is in agreement with this assessment. With appropriate re-consenting, the subject can be retreated with a 1- or 2-dose level reduction as appropriate, along with appropriate clinical follow-up as designated by the investigator.

Dose reduction levels are provided in Table 2,

Table 2: Dose Schedule and Dose Reductions - 8 mg Once Daily (QD) dosing, continuous daily dosing in 28-day cycles

Category	If dose is 8 mg:	If dose uptitrated to 9 mg:
1st dose reduction	6 mg	8 mg
2nd dose reduction	5 mg	6 mg
3rd dose reduction	4 mg	5 mg
4th dose reduction	stop	4 mg
5th dose reduction		stop

Liver Event Safety Stopping Criteria

Liver chemistry threshold stopping criteria have been established to provide safety to the subjects and to better assess the etiology of the liver event during the development of new investigational products. The liver chemistry stopping criteria include any of the following:

- ALT $\geq 3 \times$ ULN and bilirubin $\geq 2 \times$ ULN ($> 35\%$ direct bilirubin) (or ALT $\geq 3 \times$ ULN and international normalized ratio [INR] > 1.5 , if INR measured). Exception to the bilirubin elevation is made if the subject has Gilbert's disease and the elevated bilirubin is predominantly unconjugated.
- ALT $\geq 5 \times$ ULN for 2 weeks or ALT > 8 ULN.
- ALT $\geq 3 \times$ ULN if associated with the appearance or worsening of symptoms of liver injury, hepatitis or hypersensitivity such as fatigue, nausea, vomiting, right upper quadrant pain or tenderness, fever, rash or eosinophilia.
- Persistent elevation of ALT $\geq 3 \times$ ULN for ≥ 4 weeks or if ALT elevation cannot be monitored.

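### Tables 3 and 9 allow re-introduction only at two dose levels lower, while the attached footnotes also allow one level

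*Protocol*

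**What the plan says.** All of this stands in Protocol Section 3.4.

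- **Table 3, row above 10.0 mg/dL** (and/or significant change in baseline renal function and/or Grade 3 hypocalcemia). The drug is stopped for good. If the patient is benefiting and the investigator and medical monitor agree, "the drug may be re-introduced at 2 dose levels lower if appropriate". This text carries marker c, which no other Table 3 row carries.
- **Table 3, footnote c.** It describes the same exception and says that "the subject can be retreated with a 1- or 2-dose level reduction as appropriate". It adds an approval step: "Prior to re-introduction, the investigator should obtain written permission from the study medical monitor and the IRB". It also requires re-consent.
- **Table 3, row above 9.0 mg/dL.** After the hold: "Re-start treatment at the first reduced dose level".
- **Table 3, NOTE.** "The treating physicians must use clinical judgment and local standard of care to decide the best way to manage phosphate elevation".
- **Table 9, Grade 3 row.** The drug is again stopped for good. If the toxicity reverses within 4 weeks, the patient is benefiting and the monitor agrees, treatment may resume two dose levels lower. The marker is a.
- **Table 9, footnote a.** It repeats the sentence that allows one or two levels. The marker also appears in the Grade 1 row, where restart is at the next lower level.
- **Table 2** ("Dose Schedule and Dose Reductions - 8 mg Once Daily (QD) dosing, continuous daily dosing in 28-day cycles") gives the dose ladder.

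**The concern.** Each of the two rows names a single restart dose, and the footnote that qualifies the row permits a second, higher one for the same event. Both events lead to permanent discontinuation by default, so the restart dose is a dosing-safety rule. The medical monitor and the IRB must approve a restart, but they would be working from a text that gives two answers. Two similar patients could be restarted at different doses, each in line with some part of the Protocol.

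**Working it through.** The Protocol states no statistical figure on this point. The check compares the texts and then looks up each reading in Table 2.

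**Step 1: do row and footnote address the same event?** In Table 3 they do: marker c is attached to the re-introduction sentence of the row above 10.0 mg/dL and to nothing else, so the one-level option cannot be meant for a milder row. In Table 9, marker a serves Grade 1 and Grade 3, but the footnote does not assign one level to Grade 1 and two to Grade 3. For a Grade 3 event it therefore permits a one-level reduction that the row does not.

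**Step 2: where else does the sentence stand?** It also appears in the general exception to Table 1 and in the liver re-challenge text. Neither fixes a number of levels, so nothing conflicts there. The sentence is general re-challenge text that was not adapted to the two rows that do fix a number.

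**Step 3: size of the difference.** The Table 2 ladders are 9 → 8 → 6 → 5 → 4 → stop and 8 → 6 → 5 → 4 → stop. Levels are counted from the dose at the event.

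| Dose at event | Row: two levels lower | Footnote: one level lower | Difference per day | Per 28-day cycle | Footnote dose relative to row dose |
|---|---|---|---|---|---|
| 9 mg | 6 mg | 8 mg | 2 mg | 2 × 28 = 56 mg | 8/6 = 1.33 |
| 8 mg | 5 mg | 6 mg | 1 mg | 1 × 28 = 28 mg | 6/5 = 1.20 |
| 6 mg | 4 mg | 5 mg | 1 mg | 1 × 28 = 28 mg | 5/4 = 1.25 |
| 5 mg | stop | 4 mg | 4 mg | 4 × 28 = 112 mg | treated or not |
| 4 mg | stop | stop | none | none | no conflict |

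**Step 4: consistency within Table 3.** After 7.0-9.0 mg/dL the patient restarts at the same dose (with a reduction possible if the elevation persists), after more than 9.0 mg/dL at the first reduced level, and after more than 10.0 mg/dL two levels lower. With a one-level restart, a patient with no earlier reduction would resume after more than 10.0 mg/dL at 6 mg (from 8 mg) or 8 mg (from 9 mg). That is the dose of the row above 9.0 mg/dL, so the stricter restart dose in the top row would have no effect.

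**The case against.** The strongest reply is that both texts can be followed at once. Two levels lies within one or two, so a site that follows the row also satisfies the footnote, and it is natural to read the specific row as setting the dose and the footnote as setting the conditions. It stands that a path consistent with both texts exists. But the Protocol does not say that the row governs, and the footnote still permits what the row does not. The words about appropriateness in the row concern whether to restart at that dose; they do not offer one level.

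A second reply is discretion and oversight. The NOTE under Table 3 calls the table general guidelines and leaves phosphate management to clinical judgment. Restart needs benefit, monitor agreement, written monitor and IRB permission, and re-consent. Under either reading the restart dose is at most 8 mg, the starting dose, and is below the dose at the event. All of that stands and keeps the impact small. The NOTE gives no restart dose, however, and Table 9 has no such note.

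A third reply is that the document does not show which text was intended, and that for a patient at 5 mg the footnote keeps a restart at 4 mg possible. This stands as a cost of the fix.

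Four stronger or different readings are tempting but not supported:

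- A reader might infer that only Table 3 is affected, because footnote a in Table 9 serves two grades. The argument that each row picks its own dose from the footnote's range would clear Table 3 just as well. If it fails there, it fails for Table 9 Grade 3.
- A reader might size the problem from Section 1.3, where "by Day 28 approximately 13% of subjects may reach a phosphate level" of at least 7 mg/dL, and from "Accrual Goal: 35": 0.13 × 35 = 4.6, about 5 patients. That figure concerns a lower threshold, follows a sentence about 6 mg dosing, stops at Day 28, and covers neither the renal and hypocalcemia triggers nor eye events. It does not size this problem.
- A reader might infer that a site could choose the higher dose alone. The approval step rules that out.
- A reader might infer an effect on the trial's design or analysis. None of the figures there depends on this rule.

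**Conclusion.** The inconsistency is real and occurs in two places: Table 3 above 10.0 mg/dL with footnote c, and Table 9 Grade 3 with footnote a. The footnote's one-level dose is 20% to 33% above the row dose for patients on 6 to 9 mg. For a patient on 5 mg the two texts differ on whether treatment resumes at all.

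The impact is minor. I assume that cases will be few; the document gives no rate for phosphate above 10.0 mg/dL. The dose comparison assumes that levels are counted down Table 2 from the dose at the event. Preferring the row is a judgment that rests on the graded structure of Table 3 and on the footnotes being general text. Both footnotes also point to a Section 16.2.3, which this subprotocol does not contain. If such text exists elsewhere and settles the dose, the point reduces to a missing cross-reference.

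**What to change.** In Table 3 footnote c, replace the one- or two-level wording with *a 2-dose level reduction*. In Table 9 footnote a, add that the reduction given in the row governs: the next lower level for Grade 1, two levels lower for Grade 3. The general exception to Table 1 and the liver re-challenge text need no change.

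The cost is one phrase and one half-sentence, with no change to design, sample size, visits or analysis. The one downside is that a patient at 5 mg could not restart after a Table 3 event above 10.0 mg/dL or a Grade 3 eye event, which agrees with the rows as written. A patient at 4 mg loses nothing, because one level lower is already stop. If the authors want to keep 4 mg available to patients at 5 mg, they should say so explicitly in both places.
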